## 4.2 Exclusion Criteria

- Patients who do not meet the criteria of performance status = 2 on the ECOG Performance scale (Appendix 1) i.e. patients should not be ambulatory and able to carry out work of a light or sedentary nature e.g. light house work, office work.
- Untreated symptomatic brain or leptomeningeal metastatic disease.
- Medical or psychiatric conditions compromising informed consent.
- Any medical condition which in the opinion of the Investigator would compromise the ability of the patient to participate in the trial or which would jeopardise compliance with the protocol.
- Patient who has had chemotherapy, radioactive or biological cancer therapy within 4 weeks prior to the first dose of trial therapy, or who has not recovered to CTCAE grade 1 or better from the Adverse Event (AE) due to cancer therapeutics administered more than 4 weeks earlier. Patient who has had erlotinib, gefitinib, afatinib, or crizotinib within 1 week prior to the first dose of trial therapy, or who has not recovered to CTCAE Grade 1 or better from the AE due to any of these drugs administered more than 1 week earlier. Patient who has had ipilimumab therapy may be enrolled if requirements specified in Inclusion Criterion are met.
- Active autoimmune disease that has required systemic treatment in past 2 years (i.e. with use of disease modifying agents, corticosteroids or immunosuppressive drugs). Replacement therapy (e.g. thyroxine, insulin, or physiologic corticosteroid replacement therapy for adrenal or pituitary insufficiency, etc.) is not considered a form of systemic treatment.
- Has a diagnosis of immunodeficiency or is receiving systemic steroid therapy or any other form of immunosuppressive therapy within 7 days prior to the first dose of trial treatment. Replacement therapy (e.g. thyroxine, insulin, or physiologic corticosteroid

replacement therapy for adrenal or pituitary insufficiency, etc.) is not considered a form of systemic treatment.

- Patient has risk factors for bowel obstruction or bowel perforation (examples include but not limited to a history of acute diverticulitis, intra-abdominal abscess and abdominal carcinomatosis).
- Patient has a known history of malignancy, unless the patient has undergone potentially curative therapy with no evidence of that disease for 3 years.
- Has a history of non-infectious pneumonitis requiring steroids or has active pneumonitis or significantly reduced transfer coefficient (KCO).
- Female patients of child bearing potential should be using adequate contraceptive measures, should not be breast feeding and must have a negative pregnancy test prior to start of dosing.
- Patient previously had a severe hypersensitivity reaction to treatment with another monoclonal antibody.
- Patient had prior treatment targeting PD-1: PD-L1 axis.
- Patient is positive for Human Immunodeficiency Virus (HIV) (HIV 1/2 antibodies), active Hepatitis B (HBsAg reactive) or Hepatitis C (HCV RNA (qualitative) is detected); patients with negative Hepatitis C antibody testing may not need RNA testing.
- Known history of tuberculosis.
- Patient has an active infection requiring therapy.
- Has received a live vaccine within 30 days prior to the first dose of trial treatment.
- Patient is, at the time of signing informed consent, a regular user (including “recreational use”) of any illicit drugs or had a recent history (within the last year) of substance abuse (including alcohol).
- Patients with symptomatic ascites or pleural effusion. A patient who is clinically stable following treatment for these conditions (including therapeutic thoraco- or paracentesis) is eligible.
- Any of the following cardiac criteria:
  - Mean resting corrected QT interval (QTc) >470 msec obtained from 3 consecutive ECGs
  - Any clinically important abnormalities in rhythm, conduction or morphology of resting ECG e.g., complete left bundle branch block, third degree heart block
  - Any factors that increase the risk of QTc prolongation or risk of arrhythmic events such as heart failure, hypokalaemia, congenital long QT syndrome, family history of long QT syndrome or unexplained sudden death under 40 years of age or any concomitant medication known to prolong the QT interval.

## 4.3 Contraception

### 4.3.1 Women of childbearing potential

Women of childbearing potential are defined as women who have not had a hysterectomy and oophorectomy. Women with amenorrhea for <2 years will only be considered not to be of reproductive potential if they have a documented Follicle-Stimulating Hormone (FSH) value in the postmenopausal range.

Adequate contraception should be used from the time of screening, during the trial and for at least 90 days after completion of treatment.

Acceptable methods of contraception include total abstinence (if this is the patient's usual and preferred lifestyle choice), tubal ligation, combined oral, transdermal or intra-vaginal hormonal contraceptives, medroxyprogesterone injections (e.g. Depo-provera), copper-

banded intra-uterine devices, hormone impregnated intra-uterine systems and vasectomised partners. All methods of contraception (with the exception of total abstinence) should be used in combination with the use of a condom by their male sexual partner for intercourse.

#### 4.3.2 Males

Male patients with sexual partners who are pregnant or who could become pregnant (i.e. women of child-bearing potential) should use a condom during sexual intercourse during the trial and for at least 90 days after completion of treatment.

### 5 SCREENING AND CONSENT

#### 5.1 Screening

Patients attending oncology clinic with a diagnosis of NSCLC and a PS2, and who in the Investigator's opinion would be potentially suitable for clinical trial entry will be screened for entry onto the trial. If informed consent is given, PD-L1 expression will be measured from either an archived biopsy if available, or a newly obtained biopsy. A repeat biopsy will not be required if the PD-L1 status has already been obtained from a nationally recognised and MSD-approved laboratory. Sites must send an anonymised copy of Pathology report to confirm PD-L1 testing during screening to the PePS2 Trial Office, before the patient can be registered.

The Investigator will also conduct a full screening evaluation to ensure that the patient satisfies all inclusion and exclusion criteria. Investigators must keep a pre-screening log of all patients who receive a Patient Information Sheet, a screening log of all patients who consent to the trial and a pre-registration screening log of all patients who have tumour tissue sent for PD-L1 testing for the PePS2 trial.

Patients' whose PD-L1 status was determined prior to the PePS2 trial will still need a screening number from the Pre-Registration Screening Log and will also need to complete the Pre-Registration Screening Form and enter date PD-L1 results obtained. Regular recruitment updates will be circulated to site staff.

#### 5.2 Informed Consent

It is the responsibility of the Investigator or delegate specified on the Site Signature and Delegation Log to obtain written informed consent for each patient prior to performing any trial related procedure. Specific Patient Information Sheets are provided to facilitate this process. Investigators must ensure that they adequately explain the aim, trial treatment, anticipated benefits and potential hazards of taking part in the trial to the patient. The Investigator should also stress that the patient is completely free to refuse to take part or withdraw from the trial at any time. The patient should be given ample time to read the Patient Information Sheet and to discuss their participation with others outside of the site research team. The patient must be given an opportunity to ask questions which should be answered to their satisfaction. The right of the patient to refuse to participate in the trial without giving a reason must be respected.

If the patient expresses an interest in participating in the trial they should be asked to sign and date the latest version of the Informed Consent Form. The Investigator or delegate must then sign and date the form. A copy of the Informed Consent Form should be given to the patient, a copy should be filed in the hospital notes, and the original placed in the Investigator Site File (ISF). Informed consent should be obtained within 28 days of starting treatment; otherwise it will be necessary to re-consent the patient. Once the patient is entered into the

trial the patient's Trial Number (TNO) should be entered on the Informed Consent Form maintained in the ISF. In addition, if the patient has given explicit consent by signing the copy of the Informed Consent Form a copy of the signed Informed Consent Form must be sent in the post to the PePS2 Trial Office for review. Details of the informed consent discussions should be recorded in the patient's medical notes, this should include date of, and information regarding, the initial discussion, the date consent was given, with the name of the trial and the version number of the Patient Information Sheet and Informed Consent Form. Throughout the trial the patient should have the opportunity to ask questions about the trial and any new information that may be relevant to the patient's continued participation should be shared with them in a timely manner. On occasion it may be necessary to re-consent the patient, in which case the process above should be followed and the patient's right to withdraw from the trial respected.

Electronic copies of the Patient Information Sheet and Informed Consent Form are available from the PePS2 Trial Office and should be printed or photocopied onto the headed paper of the local institution.

Details of all patients approached about the trial should be recorded on the Patient Screening/Enrolment Log and with the patient's prior consent their General Practitioner (GP) should also be informed that they are taking part in the trial. A GP Letter is provided electronically for this purpose.

## **5.2.1 Screening Investigations**

### ***5.2.1.1 Histologically Confirmed PD-L1 status***

As part of the pre-screening registration process, PD-L1 testing may be carried out on an archival biopsy sample if available or a newly obtained biopsy, at a nationally recognised MSD-approved laboratory for PD-L1 staining. Repeat biopsies are not required if the PD-L1 status is already known (see section 5.1).

Biopsies taken for PePS2 may be obtained by Endobronchial ultrasound (EBUS) or Computer-Tomography (CT)-guided. Five slides fresh cut sections from Formaldehyde Fixed Paraffin Embedded (FFPE) tissue will be assessed by the site Pathologist for PD-L1 testing with >50% tumour content and at least 50 viable neoplastic cells overall. These slides will then be shipped to an MSD-approved laboratory for PD-L1 testing and the Trial Office will inform sites of successful staining. The PD-L1 status of the patient must be known for patient to be eligible for the trial. The only exception to this will be patients who have submitted to a repeat biopsy for the explicit purpose of ascertaining the PD-L1 status in the PePS2 trial and where PD-L1 staining has failed on that repeat biopsy.

### ***5.2.1.2 Screening Assessments***

Please see Table 1 Schedule of Assessments, Table 2 Routine Laboratory Tests and the Treatment Assessments flowchart for detailed description of the procedures and tests. After written informed consent is obtained, the following screening procedures must take place:-

Up to 28 days prior to trial treatment:

- Medical history – Radiographic studies performed prior to study trial entry may be collected for review by the Investigator.
- Prior Medications
- ECOG assessment

- Coagulation parameters
- CT scan with contrast (RECIST v1.1 reporting – Appendix 2)
- ECG
- HIV, Hepatitis B and C testing
- Tumour biopsy if archived tissue is not available

Up to 7 days prior to trial treatment

- Physical exam
- Charlson Index
- Vital signs
- Concomitant medications
- ECOG assessment
- Haematology
- Urinalysis
- Clinical chemistry
- Renal function - GFR
- Thyroid function and cortisol

Within 72 hours of first dose of pembrolizumab

- Pregnancy test if applicable

## 5.2.2 Patient Screening Log

The following details of all patients screened for participation in this trial will be collected:

- Screening number
- Date screened
- Date of Birth
- Sex
- Whether the patient was eligible and reasons for ineligibility
- Whether the patient gave written informed consent
- Whether the person was registered
- Reasons(s) patient was not registered

## 6 TRIAL ENTRY

Prior to recruitment of patients into the trial, the Principal Investigator for each site, or their delegate, should have returned all required documentation to the PePS2 Trial Office, and the site personnel involved with the trial must have received appropriate training from the Trial Coordinator.

### 6.1 Patient Registration

Patients must be registered with the PePS2 Trial Office at Cancer Research UK Clinical Trials Unit (CRCTU) at the University of Birmingham.

- Prior to trial entry, sites should complete the first page of the Pre-Registration Screening Form and phone the Trial Office to
  - give the site-specific screening number from the pre-registration screening log
  - confirm and email an anonymised pathology report with PD-L1 results from an archived tissue or
  - confirm that slides from a newly obtained biopsy will be sent with the Pre-Registration Screening Form to an MSD-approved laboratory for PD-L1 staining.

- After all eligibility criteria have been met, participating sites must fax copies of the Eligibility Forms to the PePS2 Trial Office and the patient's eligibility will be confirmed at registration.
- Sites must then telephone the registration line with the details required on the Registration Form and the patient will be registered over the phone and allocated a Trial Number (TNO). The registration line will be open during office hours, 9am-5pm, Monday-Friday.
- A fax will be sent to the main site administrator and Pharmacy confirming the details of registration. Trial drug prescriptions must include the patient's TNO and dose.
- Sites should post a copy of the Informed Consent Form to the PePS2 Trial Office.

**[contact]**

## 7 TREATMENT DETAILS

### 7.1 Details of Investigational Medicinal Product

Pembrolizumab is an Investigational Medicinal Product (IMP) for the purposes of this trial. Full details of the IMP are contained in the PePS2 Pharmacy Manual, which also lists the Pharmacist's responsibilities, details of labelling, record keeping for prescribing, dispensing, and accountability of the IMP. The PePS2 Pharmacy Manual will be sent to the responsible Pharmacist.

### 7.2 Investigational Medicinal Product Supply

Pembrolizumab will be supplied, packaged and delivered to sites by Almac. See the PePS2 Pharmacy Manual for further information.

### 7.3 Pembrolizumab Administration

Pembrolizumab will be administered as a 30 minute IV infusion, with a window of -5 and +10 minutes, at a flat dose of 200 mg. A dosing interval every 3 weeks (Q3W) will be employed. See the PePS2 Pharmacy Manual for further information about pembrolizumab.

**Table 3: Dosing Instructions for pembrolizumab.**

Drug	Dose/ Potency	Dose Frequency	Route of Administration	Regimen/ Treatment Period	Use
Pembrolizumab	200 mg flat dose	Q3W	30 minute IV infusion	For 2 years or until progression	Experimental

### 7.4 Treatment Schedule

For details please refer to the Table 1: Schedule of Events (see page x) and the Treatment Assessments Schedule (see page 14).

[figure not shown]
Patients will be administered pembrolizumab for up to 2 years or until progression; each cycle being 21 days. Trial treatment should be administered on day 1 of each cycle after all procedures/assessments have been completed as detailed on the Trial Schema. Trial treatment may be administered up to 3 days before or after the scheduled day 1 of each cycle due to administrative reasons. Trial treatments will be administered on an outpatient basis.

Patients with unacceptable toxic side effects from pembrolizumab will come off treatment until disease progression.

In the case of CR it is at the discretion of the Investigator to keep a patient on trial treatment or to discontinue trial treatment based on the following guidelines. This decision will be based on the clinical judgment of a patient's overall clinical condition, including performance status, clinical symptoms, and laboratory data. Patients who have a confirmed complete response by two scans  $\geq 4$  weeks apart and who have been on pembrolizumab treatment for at least 6 months may discontinue pembrolizumab treatment at the discretion of the Investigator after receiving at least two doses beyond the initial determination of CR. Pembrolizumab may be resumed upon disease recurrence in these patients.

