**Table 4: Dose modification and toxicity management guidelines for immune-related AEs associated with pembrolizumab**

Immune-related AEs	Toxicity grade or conditions (CTCAEv4.0)	Action taken to pembrolizumab	AE management with corticosteroid  and/or other therapies	Monitoring and Supportive Care
Pneumonitis	Grade 2	Withhold 	
 
Administer corticosteroids (initial dose of 1-2mg/kg prednisone or equivalent) followed by taper
 
	
 
Monitor subjects for signs and symptoms of pneumonitis
 
Evaluate subjects with suspected pneumonitis with radiographic imaging and initiate corticosteroid treatment
 
Add prophylactic antibiotics for opportunistic infections
 

	Grade 3 or 4, or recurrent Grade 2	Permanently discontinue		
Diarrhoea / Colitis	Grade 2 or 3	Withhold	
 
Administer corticosteroids (initial dose of 1-2mg/kg prednisone or equivalent) followed by taper
 
	
 
Monitor subjects for signs and symptoms of enterocolitis (i.e. diarrhea, abdominal pain, blood or mucus in stool with or without fever) and of bowel perforation (i.e. peritoneal signs and ileus).
 
Subjects with <math>\geq</math> Grade 2 diarrhea suspecting colitis should consider GI consultation and performing endoscopy to rule out colitis.
 
Subjects with diarrhea/colitis should be advised to drink liberal quantities of clear fluids. If sufficient oral fluid intake is not feasible, fluid and electrolytes should be substituted via IV infusion.
 

	Grade 4 or recurrent Grade 3	Permanently discontinue		
AST / ALT elevation or Increased Bilirubin	Grade 2	Withhold	
 
Administer corticosteroids (initial dose of 0.5- 1mg/kg prednisone or equivalent) followed by taper
 
	
 
Monitor with liver function tests (consider weekly or more frequently until liver enzyme value returned to baseline or is stable)
 

	Grade 3 or 4	Permanently discontinue		

Immune-related AEs	Toxicity grade or conditions (CTCAEv4.0)	Action taken to pembrolizumab	AE management with corticosteroid  and/or other therapies	Monitoring and Supportive Care

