Immune-related AEs	Toxicity grade or conditions (CTCAEv4.0)	Action taken to pembrolizumab	AE management with corticosteroid  and/or other therapies	Monitoring and Supportive Care
or toxic epidermal necrolysis (TEN) suspected	Confirmed SJS or TEN	Permanently discontinue		
Myocarditis	Grade 1 or 2	Withhold	
 
Based on severity of AE administer corticosteroids
 
	
 
Ensure adequate evaluation to confirm etiology and/or exclude other causes
 

	Grade 3 or 4	Permanently discontinue		
All Other immune-related AEs	Intolerable/persistent Grade 2	Withhold	
 
Based on severity of AE administer corticosteroids
 
	
 
Ensure adequate evaluation to confirm etiology or exclude other causes
 

	Grade 3	Withhold or discontinue based on the type of event 		
	Grade 4 or recurrent Grade 3	Permanently discontinue		

*Footnotes: General Instructions for management of irAE*

1. Corticosteroid taper should be initiated upon AE improving to Grade 1 or less and continue to taper over at least 4 weeks.
2. For situations where pembrolizumab has been withheld, pembrolizumab can be resumed after AE has been reduced to Grade 1 or 0 and corticosteroid has been tapered. For subjects with Grade 3 or 4 immune-related endocrinopathy, pembrolizumab may be resumed when AE improves to Grade 2 or lower and is controlled with hormonal replacement therapy.
3. For situation where pembrolizumab is withheld initially, pembrolizumab should be **permanently discontinued** if AE does not resolve within 12 weeks of last dose or corticosteroids cannot be reduced to ≤ 10 mg prednisone or equivalent per day within 12 weeks.
4. For severe and life-threatening irAEs, IV corticosteroid should be initiated first followed by oral steroid. Other immunosuppressive treatment should be initiated if irAEs cannot be controlled by corticosteroids.
5. Events that require discontinuation include and not limited to: Gullain-Barre Syndrome, encephalitis

**Note:** For participants with Grade 3 or 4 immune-related endocrinopathy where withhold of pembrolizumab is required, pembrolizumab may be resumed when AE resolves to ≤ Grade 2 and is controlled with hormonal replacement therapy or achieved metabolic control (in case of T1DM).

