### 7.11 Patient Withdrawal

The Investigator will make every reasonable effort to keep each patient on trial. However, if the Investigator removes a patient from the trial treatment or if (s)he declines further participation final assessments will be performed, if possible. All the results of the evaluations and observations, together with a description of the reasons for trial withdrawal, must be recorded in the CRF. For patients withdrawing from trial treatment for reasons other than withdrawal of consent or due to disease progression then continue with RECIST 1.1 scans until documented progression as per protocol. For patients who have come off treatment due to unacceptable toxicity, CT scans will be performed every 9 weeks until disease progression or until the patient starts another anti-cancer treatment. CT scans are to be reported according to RECIST v1.1 criteria (see Appendix 2).

Following assessment by the Principal Investigator and discussion with the PePS2 Trial Office, patients who meet RECIST criteria for progressive disease (PD) may be continued on trial treatment if the treatment is tolerable and believed to be of clinical benefit. Documentation of continued clinical benefit should be recorded in the patient's medical notes by an Investigator.

In the event of a patient's decision to withdraw from the trial, the Investigator must ascertain from which aspects of the trial the patient wishes to withdraw, and record the details on the Withdrawal CRF. All patients will continue to be followed-up, and all information and tissue samples collected up until the point of withdrawal, will be retained and analysed.

Patients who withdraw from the trial due to AEs (clinical or laboratory) will be treated and followed according to accepted medical practice. All pertinent information concerning the outcome of such treatment must be recorded in the CRF.

The following are justifiable reasons for the Investigator to withdraw a patient from trial:

- Unacceptable toxicity
- Unforeseen events: any event which in the judgement of the Investigator makes further treatment inadvisable
- SAE requiring discontinuation of treatment
- Withdrawal of consent
- Serious violation of the trial protocol (including persistent patient attendance failure and persistent non-compliance)
- Withdrawal by the Investigator for clinical reasons not related to the trial drug treatment

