Grades 3 or 4 
Grade 3: Prolonged (i.e., not rapidly responsive to symptomatic medication and/or brief interruption of infusion); recurrence of symptoms following initial improvement; hospitalization indicated for other clinical sequelae (e.g., renal impairment, pulmonary infiltrates)
 
Grade 4: Life-threatening; pressor or ventilatory support indicated
	
Stop Infusion.
 
Additional appropriate medical therapy may include but is not limited to:
 
Epinephrine** IV fluids Antihistamines NSAIDs Acetaminophen Narcotics Oxygen Pressors Corticosteroids
 
Increase monitoring of vital signs as medically indicated until the subject is deemed medically stable in the opinion of the investigator. Hospitalization may be indicated.
 
**In cases of anaphylaxis, epinephrine should be used immediately.
 
Subject is permanently discontinued from further study drug treatment.
	
No subsequent dosing

---	---	-----------------------------

Appropriate resuscitation equipment should be available at the bedside and a physician readily available during the period of drug administration.

For further information, please refer to the Common Terminology Criteria for Adverse Events v4.0 (CTCAE) at <http://ctep.cancer.gov>

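### Protocol Section 7.4, read literally, ends the treatment break for unacceptable toxicity at disease progression, which conflicts with the protocol's own discontinuation, resumption and dosing-duration rules

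*Protocol*

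**What the plan says.** The sentence at issue is in Protocol Section 7.4: "Patients with unacceptable toxic side effects from pembrolizumab will come off treatment until disease progression". It names no scan, visit or other follow-up action, and it does not refer to Section 7.5.

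The other provisions that bear on it are these:

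- **Duration of dosing.** Section 7.4 also says "Patients will be administered pembrolizumab for up to 2 years or until progression; each cycle being 21 days", and Table 3 gives the treatment period as "For 2 years or until progression".
- **Immune-related toxicity.** Table 4 (Section 7.5) lists conditions with the action "Permanently discontinue". Where dosing is only withheld, footnote 2 says "pembrolizumab can be resumed after AE has been reduced to Grade 1 or 0 and corticosteroid has been tapered", with a separate grade condition for endocrinopathies. Footnote 3 turns a withheld dose into permanent discontinuation "if AE does not resolve within 12 weeks of last dose", or if steroids cannot be brought down to a stated level in 12 weeks.
- **Infusion reactions.** For Grade 3 or 4, Table 6 says "Subject is permanently discontinued from further study drug treatment".
- **Appendix 7.** Permanent discontinuation is required for a recurrent Grade 3 or any Grade 4 immune-related reaction, except endocrinopathies controlled with hormone replacement.
- **Imaging after a toxicity stop.** Section 7.11 says "For patients who have come off treatment due to unacceptable toxicity, CT scans will be performed every 9 weeks until disease progression", or until another anti-cancer treatment starts. Table 1 footnote 20 agrees.
- **Pointer.** Section 7.11 sends the reader to Section 7.5 for the details of discontinuation.

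**The concern.** The word *until* fixes the end of a period. In this sentence the period is time off treatment and its end is progression, so the literal meaning is that the bar on dosing lifts when the disease progresses. A site that acted on Section 7.4 alone could give pembrolizumab again to a patient who had stopped for intolerable toxicity, where other parts of the same protocol require a permanent stop or set different conditions for restarting.

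The literal reading is not absurd in context. The next paragraph of Section 7.4 describes patients who stop and may later resume at recurrence (complete responders), and Section 7.11 allows some dosing beyond RECIST progression. A reader therefore meets dosing after progression elsewhere in the protocol, once in the very next paragraph. What is at stake is the safety of patients who stop for toxicity and whether sites all follow one rule.

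**Working it through.** No figure in the plan depends on this sentence, so there is nothing to recompute. The check is a comparison of the provisions, asking two questions of each: what does progression do, and what decides whether dosing may restart after toxicity?

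| Provision | What progression does | What governs restarting after toxicity |
|---|---|---|
| Section 7.4, toxicity sentence (literal) | Ends the time off treatment | Progression |
| Section 7.4 duration rule; Table 3 | Ends dosing | Not addressed |
| Table 4, permanent-discontinuation rows | No role | No restart |
| Table 4, withhold rows with footnotes 2 and 3 | No role | Event grade and steroid taper, within a 12-week limit |
| Table 6, Grade 3 or 4, and Grade 2 despite premedication | No role | No restart |
| Appendix 7, recurrent Grade 3 or any Grade 4 immune-related reaction | No role | No restart (controlled endocrinopathies excepted) |
| Section 7.11; Table 1 footnote 20 | Ends CT scanning, unless a new cancer treatment starts first | Not addressed |

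Four things follow.

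1. *Conflict with permanent discontinuation.* The first row cannot stand with the permanent-discontinuation rows of Table 4, with Table 6 or with Appendix 7. Unacceptable toxicity is not tied to a CTCAE grade in Section 7.4, so this direct conflict covers the events that fall under those rules.
2. *Conflict on the trigger for resumption.* Against the withhold rows of Table 4 the disagreement is narrower. Both allow a return to treatment, but Table 4 ties it to recovery and Section 7.4 to progression.
3. *Conflict on the meaning of progression.* In Table 3 and the duration rule, progression closes dosing; in the toxicity sentence it closes the break from dosing. Table 3 has no toxicity rule of its own, so this is a different conflict from the first. Nor is its end point absolute. Section 7.11 permits continuation beyond progression if treatment is tolerable, after assessment by the Principal Investigator and discussion with the Trial Office, and Section 7.4 permits resumption after a complete response. Neither provision covers a restart at progression after stopping for unacceptable toxicity.
4. *Likely origin.* The last row uses the same population and the same end point, with CT scanning as the activity that continues. The Section 7.4 sentence reads like that rule with the scanning left out.

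Each outcome was then checked for any effect of re-treatment at progression:

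- **Toxicity co-primary** (Protocol Section 2.2.1.1, SAP Section 9.1.1): a treatment-related delay or a discontinuation already counts, so a patient who stopped for treatment-related toxicity has the event whatever happens later.
- **Durable clinical benefit:** requires no prior progression, so dosing after progression cannot create a success.
- **TTP and PFS:** the event has already occurred at recorded progression.
- **Cycles received (SAP Section 6), adverse event summaries (SAP Section 8) and OS (SAP Section 9.1.2.5):** these could change, but only for patients actually re-treated.

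**The case against.** The strongest reply is that no competent site would act on the literal reading. The sentence does not say that treatment resumes. Where the authors meant resumption, in the next paragraph, they said so expressly and limited it to complete responders. Section 7.11 directs the reader to Section 7.5 for discontinuation, and Tables 4 and 6 and Appendix 7 state permanent stops in plain terms. Section 7.11's allowance for dosing beyond progression requires that treatment be tolerable, a condition that a patient stopped for unacceptable toxicity would not obviously meet.

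Most of this stands. It makes a drafting slip the probable explanation, and it means that the documents do not support an inference that the protocol intends re-treatment at progression after toxicity.

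It does not remove the point. The pointer to Section 7.5 is in Section 7.11, not in Section 7.4, and no order of precedence is stated. The provisions behind it are not uniform either. For an event unresolved at 12 weeks, Table 4 footnote 3 calls for permanent discontinuation, whereas Appendix 7 asks only that discontinuation be considered after discussion with the Trial Office. A safety instruction should not have to be reconstructed from other sections.

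**Conclusion.** The inconsistency is real and should be corrected. It is more than clerical, because the sentence is an operative instruction about stopping treatment for toxicity and its literal meaning contradicts explicit rules elsewhere. It is less than a design flaw: the 60-patient sample size, the BEBOP decision thresholds and the operating characteristics are untouched. The effect is on patient safety and on consistency of site instructions, with at most minor effects on cycle counts, adverse event summaries and OS.

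Two stronger readings might be inferred, and neither is supported. One is that re-treatment would blur the toxicity co-primary; it would not, because the delay or discontinuation has already been counted. The other is that the number of affected patients can be derived from the plan's prior toxicity rate. That rate, about 20%, gives 60 × 0.20 = 12 patients with a delay or a discontinuation combined. The documents do not split the two, and do not say how many such patients would progress or be re-treated, so no count follows.

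The conclusion rests only on the wording of the current protocol. It takes no position on which clinical rule is right.

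**What to change.** Reconcile the Section 7.4 toxicity sentence with Table 1 footnote 20, Table 3, Section 7.5 and Table 4 (including footnotes 2 and 3), Section 7.11, Table 6 and Appendix 7. State two things separately: the rule for stopping treatment, by cross-reference to Section 7.5 with Table 4 and to Table 6; and the rule for continuing CT scans after a toxicity stop, by cross-reference to Section 7.11. Progression should then be attached only to whatever the sponsor means it to govern. Since the cross-reference leads to provisions that differ on events unresolved at 12 weeks, Table 4 footnote 3 and Appendix 7 should be aligned at the same time. The choice of clinical rule is for the sponsor and investigators.

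The cost is one sentence in Section 7.4, plus the alignment of the 12-week wording, in a protocol amendment. No visit, assessment or analysis is added, and the SAP needs no change.
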